3.3 STUDY DESIGN

This research will utilize a mixed-methods exploratory sequential design, incorporating both quantitative surveys and qualitative interviews. Exploratory because aspects of the qualitative aspects will be used to adjust the design of the YoFA training program which

will help develop a comprehensive program for such a program among SSC. The next design is a cross-sectional design with pre and post-tests to both the interventional and control groups to obtain a general baseline in both districts and assess the impact of the YoFA program.

3.3.1 Qualitative Part

Discussions or interviews on perspectives of individuals and groups of individuals regarding the acceptability and usability of FA-trained kids within the school and in the community. It will also seek to understand their thoughts on incorporating an FA training program within the school curriculum. It will be conducted with key stakeholders, including school administrators, and community leaders as well as students of the school.

It will precede the qualitative part and include Focused group discussions (FGDs), in-depth interviews of certain community and administrative stakeholders within the school and observations of scenarios.

3.3.2 Quantitative Part:

The quantitative aspect will involve administering questionnaires to students to assess their knowledge, attitudes (confidence), and practices (utilisation/usability) of FA trauma/injury skills before and after their training. This will focus mostly on staying safe, calling for help and stopping a life-threatening bleed. The intervention will include training the intervention group in reasonable clusters on the same subject matter and assessing the change in KAPs before and after the intervention. It will also include scenarios to test the efficacy of participants in carrying out the First Aid Act.

PERIOD OF STUDY

The study will be a 10-month study from September 2024 to July 2025 including administrative and ethical clearance needed.

3.4 ELIGIBILITY CRITERIA

3.4.1 Inclusion Criteria

For the Quantitative part

- Form one (1) to three (3) students (ages 10 to 14 years) in the four (4) state secondary schools (SSS) in Tiko and Buea health districts who are willing to participate in the study.
- Students officially enrolled in the school for the academic year
- Those students whose parents consent for their children to be part of the study.

For the Qualitative part

- Stakeholders within the educational care system – Principals, community leaders, and parents who consent to be part of the study.
- Students whose parents give parental consent for their children to participate in the study.

3.4.2 Exclusion Criteria

- Any child who is not in forms 1 to 3 (10 to 14 years old) in the selected schools
- Any student who misses any of the training sessions
- Any student who willingly backs out of the study.
- Any child whose parents do not give parental consent for them to be part of the study.

Age Limits

- For the Secondary School Children (SSC): 10 to 14 years old
- For the various stakeholders (school administrators, teachers, community leaders, and parents): Adults between 21 and 65 years.

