1.1.2 Operational Definitions

First Aid Knowledge: Measured by a standardized questionnaire assessing participants' understanding of basic first aid principles, including recognition of injuries, appropriate responses, and the use of first aid equipment. A pre-test and post-test will be administered to evaluate knowledge gained from the training.

Practical Skills Proficiency: Evaluated through hands-on assessments where participants (children) demonstrate specific first aid techniques, such as identification of injuries including wounds and take action towards care. Proficiency will be rated on a scale from 1 to 5 by the trainers based on accuracy and confidence in performing the skills.

Training Attendance: Defined as the percentage of scheduled training sessions attended by each participant. Attendance will be tracked through a sign-in sheet at each

session, with a minimum attendance threshold set at 80% to qualify for the evaluation phase.

Behavioral Intent to Use First Aid: Assessed using a Likert scale survey administered after the training program, measuring participants' self-reported likelihood of applying first aid skills in real-life situations. This will include scenarios where they might encounter injuries or emergencies.

Community Engagement: Measured by the number of community members who give favourable feedback on the activities of the YoFA trainees during and after the intervention. The effectiveness of these activities will be evaluated through feedback forms from community members.

Self-Efficacy in First Aid: Evaluated using a self-report scale that assesses participants' confidence in their ability to perform first aid tasks taught. This will be measured before and after the training program to determine changes in self-efficacy levels.

Injury Response Time: Measured by timing participants' responses in simulated emergency scenarios during training sessions. The time taken to initiate appropriate first aid measures will be recorded and analyzed to assess improvement over the course of the program.

These will help us ensure that the study effectively measures the impact of the YOFA Training Program on early secondary school children in the Fako Division, providing clear metrics for evaluation and analysis.

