3.2 STUDY POPULATION

The qualitative part will include teachers, principals and vice (of the selected schools), parents (whose kids attend the selected schools), regional delegates (of secondary education and public health) and a few community leaders like quarter heads and or chiefs of both the control and the intervention districts of Buea and Tiko.

The cross-sectional survey will involve students in the early secondary school classes (forms 1 to 3) of the selected state secondary schools (SSS) in Buea and Tiko. These classes are chosen because they have most of the children aged 10-14 years which is the age trained in most studies and we believe these ones have just crossed a milestone from the primary school to get to secondary.

The intervention part will also involve the early SSC who take part in the cross-sectional survey before and after the intervention.

The evaluation will involve all the students as well as the stakeholders in both intervention groups who had been interviewed at the start of the study to determine the impact of the YoFA training program and challenges faced. It will also include the students to assess the need for refresher courses on FA for LTB and equally identify challenges faced during the three months prior to the summative evaluation period.

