3.6 STUDY PROCEDURE

The study will use the precede proceed planning model and the ecological model described in the review of Literature following the steps below from planning the research project, through implementing the intervention, and to the monitoring and Evaluation phases.

Step 1: Preparatory/Planning Phase

The planning model to use here will be the Ecological model in conjunction with aspects of the PRECEDE-PROCEED planning model (PPPM).

The other steps of the planning phase include:

- Preparing documents to apply for ethical clearance and administrative authorizations to perform the study.
- Authorizations are needed from the Regional Delegation of Secondary Education for the SWR (1), the divisional delegates/inspectors of the aforementioned ministry (2), the School Principals (8) the Regional Delegation of Public Health

(RDPH) for the SWR (1), and the Chiefs of Health Districts (CHDs) (2)

- Constitute and train a team of 4 trainers medical doctors/students and data collectors and interviewers.
- Obtain a sample frame of students from the various classrooms of the various schools and proceed with the selection of participants as described above.
- Enlist all potential teachers and stakeholders to be interviewed

Step 2: Intervention Phase

- Organize students to be trained in groups of 10.
- Each training session will last 2.5 hours and each group will be trained for 2 days.

That is a total of 5 hours.

- Overall, it will take 6 weeks (1 month, 2 weeks) to train 3 groups of 25 students each as shown in *Table 6* below.
- The Sessions will begin with a 30-to-45-minute pretest followed by theory on day 1. Then mixed theory, video, and practical sessions on days 1 and 2. Main contents Content include: 1. responding to emergencies (first aid) and on prevention of injuries: “Call for help”, fever and contents of a first aid kit, 2. controlling Life-threatening bleeds (LTBs) and immediate first aid in burn cases, fractures, and/or dislocations in the face of LTB [11,46]. It will include the use of cartoons, simple language and memory aids:

(1) Video, (2) small group teaching, (3) demonstration manikin, (4) supervised practice.

- Interviewing the teachers, principals and other stakeholders. Interviews will be done using interview guides and tape recorders.
- For the control group, we will do a selection of the participants as described and there

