will be a session for pretesting at the beginning of the intervention, at the immediate end, and 3 months after. **During the 3 months follow up period, we will visit the schools during their Wednesday club days every 2 weeks for 30mins to 1hour, to document their experiences and challenges in real time and their use of the skills.**

The qualitative part will take place before the quantitative pretesting of both groups begins.

Table 6: Plan of training and Evaluation of intervention groups

HA	School	N	Training Period in 2024	Date for Last Evaluation, 2024
Molyko (Intervention)	BGS Molyko	25	Nov 6 th , and 13 th	Feb 5 th
		25	Nov 20 th , and 27 th	Feb 19 th
		25	Dec 4 th and 11th	March 5 th
Mutengene (Control)	GHS Mutengene	70	November 6 th	Feb 26 th
	Total	145		

Step 3: Evaluation Phase

This comprises the evaluation of students' perceptions, barriers, and challenges in learning and applying the skills and lessons learned. It will equally involve evaluating parents' and stakeholders' perceptions about the program and including FA training in school curricula. It will involve the use of evaluation forms. This will take place about the same time as the post-three-month evaluation.

Knowledge will be assessed by evaluating whether the participants have ever heard of first aid or observed situations in which first aid was needed. They will be expected to have an increase in knowledge of first aid, especially regarding calling for help, stopping acute and life-threatening bleeds (LTB), and referrals after the training.

Before the training, we expect people not to have practiced first acts ever or to have

done it in a wrong way or to be scared to carry out specific first aid acts. After the training, we expect them to be more alert and identify situations needing first aid acts. Additionally, we expect their self-efficacy and confidence to perform first aid acts to increase and to effectively carry out first aid acts within their community or the school premises that will be documented using designed forms.

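### The attendance rule removes trained pupils who miss a session but cannot act on controls, and it conflicts with the statement that all students are evaluated

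*Protocol*

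**What the plan says.** Three statements in the protocol decide who is evaluated.

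- Section 3.4.2 (Exclusion Criteria) lists "Any student who misses any of the training sessions".
- Section 1.1.2 (Training Attendance) defines attendance as a percentage of scheduled training sessions, "with a minimum attendance threshold set at 80% to qualify for the evaluation phase".
- Section 3.2 (Study Population) states: "The evaluation will involve all the students as well as the stakeholders in both intervention groups".

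On the amount of training, section 3.6 says "Each training session will last 2.5 hours and each group will be trained for 2 days", and Table 6 gives each training group two dates, for example "Nov 6 th , and 13 th". Section 3.11 refers instead to four days of training before the post-test. The trained arm is pretested within the training: "The Sessions will begin with a 30-to-45-minute pretest followed by theory on day 1". For the control group, section 3.6 describes tests only: there "will be a session for pretesting at the beginning of the intervention, at the immediate end, and 3 months after". Section 3.11 plans a difference-in-difference analysis of the change in knowledge, attitudes and practices.

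**The concern.** Attending training is something a pupil does after enrolment, and only pupils in the intervention school can do it or fail to do it. A trained pupil who sits the day-1 pretest and misses the later session is removed, although that pupil could still be tested at three months. A control pupil with the same habit of absence stays in. The comparison then sets full attenders against controls not selected on attendance.

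Difference-in-difference removes a fixed difference in level between the two groups. It does not remove a difference in expected change, and pupils who attend every session may well differ from absentees in how much they would change. The 15% dropout allowance in section 3.5 restores numbers, not comparability.

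The rule also leaves the evaluated group unsettled, because section 3.2 on its plain reading takes in every student. If the rule were applied so that excluded pupils are not tested, no later analysis plan could recover their outcomes.

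Absence on a test day can occur in either arm. It is ordinary missing data and is not part of this point.

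**Working it through.** **Step 1. Do the two attendance rules differ in effect?** Attendance = sessions attended / sessions scheduled.

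- Two sessions (section 3.6, Table 6): possible values 0%, 50%, 100%. One miss gives 50%.
- Four sessions (section 3.11, taking one per day): 0%, 25%, 50%, 75%, 100%. One miss gives 75%.

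Both fall below 80%, so at either number of sessions the 80% rule requires full attendance and removes the same pupils as section 3.4.2. The real conflict is between these two sections and section 3.2.

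**Step 2. Gap between the full-attender estimate and the all-pupil effect.** Let C be the mean change in full attenders, K the mean change in controls, a the share of pretested trained pupils excluded, and d the number of points by which their change would be smaller.

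- Full attenders against controls: C − K.
- All trained pupils against controls: (1 − a)C + a(C − d) − K = (C − K) − a × d.
- Gap: a × d.

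The documents give neither a nor d. Assumed range, set against the planned 25-point difference (section 3.5):

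| a | d (points) | a × d (points) | share of 25 |
|---|---|---|---|
| 5% | 10 | 0.5 | 2% |
| 10% | 20 | 2.0 | 8% |
| 15% | 30 | 4.5 | 18% |

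Of the 75 trained pupils ("Overall, it will take 6 weeks (1 month, 2 weeks) to train 3 groups of 25 students each"), 5% to 15% is 3.75 to 11.25, about 4 to 11 pupils. If absentees would change more than attenders, d is negative and the gap reverses. The quantity d contains two parts: what pupils lose by missing training, and how they would have differed from attenders anyway. Only the second part is selection bias, and nothing in the documents separates the two.

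**Step 3. Scale.** The standard error of the protocol's own two-proportion comparison is √(0.50 × 0.50/n + 0.75 × 0.25/n). This is 8.7 points at n = 58 per group and 7.9 at n = 70. The middle case of 2 points is about a quarter of one standard error.

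**Step 4. Cost of keeping everyone.** The protocol's figure reproduces: 0.50 against 0.75, two-sided 5%, pooled-variance test without continuity correction, gives 58 per group with power 0.802. Now assume that 10% of trained pupils miss a session and gain nothing. The difference becomes 0.90 × 25 = 22.5 points, that is 0.50 against 0.725.

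| Situation | Per group analysed | Power |
|---|---|---|
| Planned 25 points | 58 | 0.80 |
| 10% of trained pupils excluded, 25 points | 52.2 v 58 | 0.78 |
| All kept, 22.5 points | 58 | 0.71 |
| All kept, 70 enrolled (Table 5), 15% lost: 70 × 0.85 | 59.5 | 0.72 |
| All kept, 70 enrolled, no dropout | 70 | 0.79 |

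Power of 80% at 22.5 points needs 73 analysed per group. With the protocol's inflation this is 73 × 1.15 = 83.95, or about 84 enrolled, more than the 70 of Table 5 or the 75 trained pupils of Table 6. If 5% or 15% gain nothing, power at 58 per group is 0.76 or 0.65. All these figures treat pupils as independent, as the protocol's calculation does.

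**The case against.** The strongest reply has four parts.

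1. *The gap a × d is not a measure of bias.* This is right. It is an overstatement only if the target is the effect in all pupils. Research question 3 asks how efficacious the programme is, which might point to complete training. That still does not justify the rule: even for the effect of complete training, attenders selected on attendance would be compared with controls who are not. A reader might infer from the table in step 2 that the programme's effect will be inflated by up to 18%. The documents do not support that, because both inputs are assumed, the sign is open and part of the gap is real loss from missed training.

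2. *The contradiction is narrow.* This is largely right. A reader might infer that all three sections disagree, but sections 1.1.2 and 3.4.2 act alike at two or four sessions. Section 3.2 is loosely worded, and an exclusion list normally narrows a population statement. It is also arguable how far the evaluation phase in section 1.1.2 covers the three-month test, since Step 3 of section 3.6 opens with perceptions and evaluation forms before turning to knowledge and the comparison of groups. The wording still has to be settled, because the study-level exclusion in 3.4.2 stands whatever that phase covers.

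3. *Nothing says that excluded pupils go untested, and an analysis plan could deal with partial attenders.* The first part is correct, so the loss of data is conditional. But the rule is stated in the protocol as an exclusion, and an analysis plan can use only outcomes that were collected.

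4. *With one school per arm and no randomisation of pupils, keeping absentees restores no randomised comparison.* Correct. It is a separate and larger limit, and it is no reason to add an avoidable one-sided filter.

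**Conclusion.** The point holds in this form. The protocol states a post-enrolment attendance filter that acts on the trained arm only, it conflicts with the plain reading of section 3.2, and the planned analysis does not remove the resulting difference in expected change. These conclusions rest on the text and on the arithmetic of two or four sessions, the four-session case assuming one session per day.

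The size and direction of any bias cannot be derived from the documents. Under the assumed inputs the full-attender estimate differs from the all-pupil effect by 0.5 to 4.5 points, 2 points in the middle case, and this includes the effect of missed training as well as selection. A reader might also infer that the 70 pupils per group in Table 5 nearly absorb the cost of keeping everyone, at power 0.79. That holds only with no dropout; with the protocol's own 15% it is about 0.72. The matter should be corrected because the asymmetry is plain and the remedy is simple, not because a large bias has been shown.

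**What to change.** - Remove attendance as a condition for eligibility (3.4.2) and for evaluation (1.1.2), and align both with section 3.2.
- Invite every enrolled pupil to the pretest and both post-tests whatever the attendance, and analyse each pupil in the arm of the school.
- Report attendance from the sign-in sheets. Keep full attenders as a labelled sensitivity analysis, stating that it compares selected pupils with unselected controls.
- Reconcile the two-day statement (section 3.6, Table 6) with the four-day statement (section 3.11).

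The cost is a few sentences and, at an assumed 5% to 15% absence, about 4 to 11 more pupils to test. The all-pupil effect may be diluted: if 10% gain nothing, expect 22.5 points instead of 25, with power of about 0.71 at 58 analysed per group or about 0.72 for 70 enrolled after 15% dropout. The change does not resolve the limit of one school per arm.

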3.5 SAMPLE SIZE AND SAMPLING

Sample Size Calculation

For the cross-sectional study and Intervention

Assuming an equal number of control and intervention subjects, a prevalence of the outcome in the controls of 0.5, and a prevalence in the intervention group of 0.75 (an absolute increase of 25%)[17] with a power of 80% and 5% error margin, we calculated the sample size needed using STATA.

Estimated sample sizes for a two-sample proportions test Pearson's chi-squared test using STATA

$H_0: p_2 = p_1$ versus $H_a: p_2 \neq p_1$ Study parameters:

```
alpha = 0.0500
power = 0.8000
delta = 0.2500 (difference)
p1 = 0.5000
p2 = 0.7500
```

Estimated sample sizes:

N =	116
N per group =	58

If we assume a 15% drop out rate, we have a sample size of $15\% * 116 = 17.4$ Thus, sample size is $116 + 17.4 = 133.4 \approx 134$

For each group, the sample needed is therefore **N = 67 students. Sampling**

Since this is a crisis area, we will use convenience sampling to choose the Health Areas (HAs) that are secure and geographically accessible (safest) in both HDs. Out of seven (7) and eight (8) HAs in Buea and Tiko HDs respectively, there are 4 accessible HAs in each. Of these, one HA from each HD does not harbour a state secondary school (SSS).

Leaving us with 3 HAs to work with in each HD. Each of these HAs contains 1 SSS but for 1 HA from each District which has 2 SSSs. We would work with all these State schools to ensure that we get students from most of the communities around the schools, thus ensuring the representativeness of our samples. To avoid spill-over, one of the districts will be selected as intervention HD and the other as the control.

Stratified random sampling will be used to select the students for the study from a sampling frame of the list of students in each classroom concerned.

We would use probability proportionate to size to choose the specific number of students to participate in the study per classroom (A, B, and C) for each class.

[figure not shown]

Figure 5: Selection of HAs and Schools for Implementation.

*GHS-Government High School; BGS-Bilingual Grammar School; GTHS Government Technical High School; GBHS government Bilingual High School

For each school distribution of the participants will be as follows:

A) For the Qualitative part:

The qualitative part will be sampled purposively.

Table 2: Number of Participants to be chosen per school for the FGDs

Health District	Schools	FGD Category of Participant	Number per school
Buea	1-BGS Molyko	Parents (1) Teachers (1) Students (1)	3
	2-GTHS Molyko	Parents (1) Teachers (1) Students (1)	3
Tiko	1-GHS Mutengene	Parents (1) Teachers (1) Students (1)	3
	2-GTHS Ombe	Parents (1) Teachers (1) Students (1)	3
	Total		12

N.B: Each focused group discussion will be comprised of 5 to 8

Table 3: Number of Participants to be chosen per school for the In-depth interviews

Health District	Schools	Category of Participant	Number per school
Buea	3- GHS Bokwango	Parents (2) Teachers (2) School Admin (1) Students (2)	7
	4-GHS Buea Town	Parents (2) Teachers (2) School Admin (1) Students (2)	7
Tiko	1-GHS Mutengene	Parents (2) Teachers (2) School Admin (1) Students (2)	7
	3-GHS Motombolombo	Parents (2) Teachers (2) School Admin (1) Students (2)	7
	Total		28

B) For the Quantitative or intervention phase

To recruit participants and avoid spill over among initially recruited participants, it was more feasible to randomly choose one classroom from among the selected schools from which to train the students. Thus, instead of table 4 below, we will apply table 5.

Table 4: Initial plan of the YoFA training Participants.

Buea	N	Tiko	N
GHS Bokwango	15	GHS Mutengene	15
GHS Bueatown	15	GTHS Ombe	15
BGS Molyko	20	GBHS Tiko	20
GTHS Molyko	20	GHS Motombolombo	20
TOTAL			70

Table 5: Number of students to train on YoFA Program

Intervention group	School Name	Control	School Name
Buea	BGS Molyko	Tiko	GHS Mutengene
Number of Participants	70		70

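### The 80% power and 5% error in section 3.5 assume independent students, but the operative plan compares one school per arm in different districts, so between-site variance cannot be estimated and the main risk is a false-positive programme claim

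*Protocol*

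**What the plan says.** Section 3.5 of the protocol sizes the study with "Estimated sample sizes for a two-sample proportions test" (Pearson chi-squared, 0.50 against 0.75, two-sided alpha 0.05, power 0.80). The result is 58 per group, raised to 67 for 15% dropout. The inputs include no ICC, design effect or number of clusters.

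The same section allocates whole districts: "To avoid spill-over, one of the districts will be selected as intervention HD and the other as the control". It first describes wide coverage, "We would work with all these State schools to ensure that we get students from most of the communities around the schools", but then replaces the multi-school layout: "Thus, instead of table 4 below, we will apply table 5". Table 5 has 70 students at BGS Molyko (Buea, intervention) and 70 at GHS Mutengene (Tiko, control). Table 6 in section 3.6 names the same two schools.

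Section 3.11 plans a difference-in-difference for the change in knowledge, attitudes and practices. It also foresees tests between the two groups. Hypothesis 3 (section 1.6.2) is worded as a claim that the programme is effective. Section 4.1 lists two limitations, the quality of the trauma case data and the absence of private schools. It does not mention the single site per arm.

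**The concern.** A test on independent students measures the group difference against variation between students only. With one school per arm, whatever moves one school or district and not the other lies entirely within the group difference, and there are 0 degrees of freedom with which to measure it. The student-level standard error leaves this component out.

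At stake is the reading of Hypothesis 3. A significant student-level result would be taken as evidence for the programme, and the protocol's chapter on expected results intends to use the findings for decisions on scale-up and policy. If the true error rate is above 5%, the stated level overstates that evidence. No later analysis can recover a variance that the design does not identify.

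**Working it through.** **1. Reproducing the protocol's figure.** Inputs from section 3.5: p1 = 0.50, p2 = 0.75, mean 0.625, two-sided alpha 0.05, power 0.80.

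n = [1.960·√(2·0.625·0.375) + 0.842·√(0.25 + 0.1875)]² / 0.25² = (1.342 + 0.557)² / 0.0625 = 57.67, so 58 per group. Power at 58 is 80.2%. The arithmetic is right for its own assumption.

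**2. Students available.** Table 5 gives 70 per arm, and "If we assume a 15% drop out rate" gives 70 × 0.85 = 59.5. Under independence, power is 81.2% at 59.5. Table 6 lists 3 × 25 = 75 trained students; 70 is used here for both arms.

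**3. Comparison at a single time.** DE = 1 + (n − 1)·ICC, and the type I error of the unadjusted test is 2·[1 − Φ(1.96/√DE)]. With n = 59.5 and assumed ICC:

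| ICC | DE | Type I error |
|---|---|---|
| 0.01 | 1.585 | 12% |
| 0.05 | 3.925 | 32% |
| 0.10 | 6.85 | 45% |

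Only ICC = 0 gives 5%.

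**4. Planned difference-in-difference.** Take total variance 1, ICC r, cluster autocorrelation c (correlation of a site's effect between two tests) and within-student correlation w = 0.5. None of r, c and w is in the protocol; all are assumed.

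- Variance that the student-level test sees: Vw = 4(1 − r)(1 − w)/n
- True variance: Vt = Vw + 4r(1 − c)
- Type I error: 2·[1 − Φ(1.96/√(Vt/Vw))]
- Rejection rate at effect d: Φ[(d − 1.96√Vw)/√Vt], the opposite tail being negligible
- d = (1.960 + 0.842)·√(2/58) = 0.5202 SD, the standardised difference that 58 per group detects with 80% power

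Worked case, n = 59.5, r = 0.05, c = 0.8: Vw = 4·0.95·0.5/59.5 = 0.0319; Vt = 0.0319 + 4·0.05·0.2 = 0.0719; ratio 2.25; type I error 19.2%; rejection rate 73.7%.

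| ICC | c | Type I error | Rejection rate at d |
|---|---|---|---|
| any | 1 | 5.0% | 81–85% (ICC 0.01–0.10) |
| 0.01 | 0.98 to 0.8 | 5.3 to 7.8% | 81 to 79% |
| 0.05 | 0.98 to 0.8 | 6.5 to 19.2% | 82 to 74% |
| 0.10 | 0.98 to 0.8 | 8.1 to 30.5% | 82 to 71% |

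Values of c near 1 suit the immediate post-test; lower values are more plausible at three months. At ICC 0.05, changing w to 0.3 gives type I error of 6.0 to 15.4%, and w = 0.7 gives 7.5 to 26.5%.

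**5. School counts.** Section 3.4.1 speaks of students "in the four (4) state secondary schools (SSS) in Tiko and Buea health districts". The sampling text in 3.5 gives three usable health areas per district, one of which has two state schools: 2 × 1 + 2 = 4 per district, 8 in all. Section 3.6 seeks authorisation from 8 principals. Tables 5 and 6 use one school per arm.

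**The case against.** The strongest reply is that the named analysis of change is the difference-in-difference, which cancels any constant difference between the schools. With no site-specific change between tests, its 5% holds at any ICC. That stands, and at c = 0.98 the departure is modest (5.3%, 6.5% and 8.1% at the three ICC values). The single-time figures apply to the between-group tests that 3.11 also foresees and to outcomes without a matching baseline, such as skill use over the three months after training. They do not describe the main analysis. It also stands that a student-level test is valid if inference is confined to these two sites, and that the layout has stated reasons: security, spill-over, and avoiding the responder programme in Limbe. Those reasons explain the choice but do not make the sites change in parallel.

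Three stronger readings are tempting and are not supported:

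- **Power collapses.** A reader might infer power as low as 35% for the difference-in-difference (ICC 0.10, c = 0.8) or 18% for a single-time comparison (ICC 0.10). Those figures belong to a test whose critical value is corrected for a known site variance. This design cannot supply that variance, so the test cannot be run.
- **Table 6 shows bias.** On its dates, first to last test spans 91 days in each trained group and 112 days in controls (6 November to 26 February). This is a scheduling difference. It shows neither direction nor size of any site-specific drift, and the control evaluation falls within the calendar range of the trained groups' evaluations.
- **The number of schools is undetermined.** Table 5 expressly supersedes Table 4, and 8 authorisations can serve the wider qualitative work. What remains is wording that was not updated.

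**Conclusion.** The concern holds as a statement about what 80% and 5% mean in this design. Section 3.5 presents them without conditions, while Tables 5 and 6 leave between-site variance unidentifiable whatever the ICC, and neither 3.11 nor 4.1 says so. For the planned difference-in-difference, the error rate for a programme claim runs from 5% (no site-specific change) to about 30% (ICC 0.10, c = 0.8). Over the same range the test still rejects at the planned effect in about 71–85% of trials. The harm is therefore false positives, not lost power. The sizes rest wholly on assumed ICC, autocorrelation and within-student correlation; the non-estimability does not. The data can support a difference in change between two sites, which is narrower than Hypothesis 3 as worded.

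**What to change.** 1. In section 3.5, state that 80% and 5% are conditional on independent students and, for the difference-in-difference, on no site-specific change between tests. Add a small table of the type I error of the student-level test over an assumed range of ICC and cluster autocorrelation, at the number left after dropout.
2. In sections 3.11 and 4.1, state that between-site variance is not estimable with one school per arm and that p-values are conditional on these two sites. Limit the Hypothesis 3 conclusion to a difference in change between two sites.
3. As a separate minor edit, align the school wording in 3.4.1 and 3.5 with Table 5. The 91 and 112 day intervals may be noted as a scheduling difference.

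The cost is protocol wording and one table, with no added students or sites. The downside is a less favourable stated error rate and a narrower conclusion.

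### Section 3.5 adds 15% for dropout instead of dividing by 0.85, so its stated minimum of 67 per group should be 69; separately, the intervention arm is 70 in Table 5 but 75 in section 3.6 and Table 6

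*Protocol*

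**What the plan says.** Protocol section 3.5 plans the comparison as a two-group test of proportions: "Estimated sample sizes for a two-sample proportions test Pearson's chi-squared test using STATA". The inputs are 0.50 in controls, 0.75 in the intervention group, a two-sided 5% level and 80% power, with groups of the same size ("Assuming an equal number of control and intervention subjects"). The output is 58 per group, 116 in total.

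The dropout step follows: "If we assume a 15% drop out rate, we have a sample size of" 15% of 116, which is 17.4. This is added to 116 to give 133.4, rounded to 134. The section concludes: "For each group, the sample needed is therefore" 67.

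Later in section 3.5 the protocol says that Table 5 will be applied in place of Table 4. Table 5 ("Table 5: Number of students to train on YoFA Program") lists 70 pupils in one Buea school (intervention) and 70 in one Tiko school (control).

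Section 3.6, Step 2, plans "to train 3 groups of 25 students each as shown in" Table 6. That table lists three batches of 25 in the intervention school and 70 in the control school, with a total of 145.

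**The concern.** An allowance for dropout should ensure that, after the assumed loss, the required number of completers remains. Adding 15% of the evaluable number does not do this, because the 15% will be lost from the larger enrolled number. The figure that section 3.5 calls the sample needed therefore misses the section's own requirement. A team that enrolled exactly 67 per group and lost 15% would finish just under 58 per group and just under 80% power.

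The second matter is internal consistency. The number of pupils to be trained is 70 in one current table and 75 in another, with no explanation. That number decides how many parental consents to seek and how many training places to arrange. It is also the figure against which achieved enrolment will be reported.

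**Working it through.** **Inputs**, all from Protocol sections 3.5 and 3.6: p1 = 0.50, p2 = 0.75, difference 0.25, two-sided alpha 0.05 (z = 1.960), power 0.80 (z = 0.842), equal groups, dropout 15%.

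**1. The protocol's base figure.** With pooled variance and no continuity correction,

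n per group = [z(alpha) × √(2 × p̄ × (1 − p̄)) + z(power) × √(p1(1 − p1) + p2(1 − p2))]² / (p2 − p1)²

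- p̄ = 0.625, so the first root is √0.46875 = 0.6847, and 1.960 × 0.6847 = 1.342.
- The second root is √(0.25 + 0.1875) = 0.6614, and 0.842 × 0.6614 = 0.557.
- n = (1.342 + 0.557)² / 0.0625 = 57.7, rounded up to 58 per group, 116 in total.

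This matches section 3.5 exactly. A continuity correction would give 66 and a one-sided test 46, so neither was used.

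**2. The protocol's dropout step.** 116 + 0.15 × 116 = 116 + 17.4 = 133.4, rounded to 134, or 67 per group. This is n × (1 + d).

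**3. What 67 leaves.** 67 × 0.85 = 56.95 completers, about 57, against 58. The largest loss that 67 can absorb while keeping 58 is 1 − 58/67 = 13.4%, not 15%.

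**4. The corrected step.** n / (1 − d): 58/0.85 = 68.2, rounded up to 69 per group, 138 in total. Working from the total, 116/0.85 = 136.5, rounded up to 137; making this even for equal groups also gives 138.

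**5. Power after 15% loss**, same formula. For m completers per group, power = Φ[(0.25 × √m − 1.342) / 0.6614].

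| Enrolled per arm | Source | Completers per arm | Power |
|---|---|---|---|
| 67 / 67 | Section 3.5, stated minimum | 56.95 | 79.5% |
| 69 / 69 | Corrected minimum | 58.65 | 80.7% |
| 70 / 70 | Table 5 | 59.5 | 81.2% |
| 75 / 70 | Section 3.6 and Table 6 | 63.75 / 59.5 | 82.6% |

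The last row uses the version of the formula for unequal groups.

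**6. Planned arm sizes side by side.**

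| Place | Intervention | Control | Total |
|---|---|---|---|
| Table 5 | 70 | 70 | 140 |
| Section 3.6 and Table 6 | 3 × 25 = 75 | 70 | 145 |

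The two plans agree on the control arm and differ by five pupils in the intervention arm.

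**The case against.** The strongest reply is that the slip has no practical effect. Section 3.5 itself says that Table 5 will be applied, and 70 per arm exceeds the corrected 69; so does 75 and 70. The shortfall arises only at 67, which neither table uses, and even there it is about one completer per group and half a percentage point of power. The unrounded requirement is 57.7, so even 68 enrolled (57.8 completers) would give 80.1%. All of this stands, and it limits the point to a correction of the stated minimum.

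A reader might infer from the arithmetic that the trial as planned falls below 80% power. The documents do not support that: on the protocol's own assumptions, every enrolment in its tables stays above 80% after 15% loss.

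A reader might also infer that 67, 70 and 75 are three conflicting targets. That goes too far. The 67 is a calculated minimum, and planning 70 against a minimum of 67 is no contradiction. Table 4's figures already add to 70 per district (15 + 15 + 20 + 20), so 70 appears to have been carried into Table 5. Only 70 against 75 in the intervention arm conflicts.

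Nor does the unequal split in Table 6 do harm. Equal groups are a planning assumption, and five extra trained pupils raise power slightly.

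What the reply does not remove is that section 3.5 states a result its own inputs do not give. Nor does the protocol present the margin in the tables as a correction for dropout.

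**Conclusion.** The point holds as a minor correction. The stated minimum of 67 per group (134) should be 69 (138). At 67 the assumed 15% loss leaves about 57 completers instead of 58, and power of about 79.5% instead of 80%. Planned enrolment already covers the corrected figure, so the planned power is not affected under the protocol's formula. Separately, the planned intervention arm is 70 in Table 5 and 75 in section 3.6 and Table 6, and the two need to be reconciled.

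These conclusions take as given the protocol's proportions (0.50 and 0.75), a 15% loss in both arms, and a formula that treats pupils as independent individuals. Table 5 draws each arm from one school, and the formula takes no account of that. Saying that 70 covers the corrected minimum is therefore a statement about the dropout arithmetic alone. It should not be read as an endorsement of the power calculation for this design.

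**What to change.** - In section 3.5, replace the additive step with 58/0.85 = 68.2, rounded up to 69 per group, and change 134 and 67 to 138 and 69.
- State one planned size for the intervention arm, at least 69, in Table 5, section 3.6 and Table 6, and bring the Table 6 total of 145 into line with it. If batches of 25 are kept for practical reasons, Table 5 should read 75; if 70 is the plan, the batch sizes in section 3.6 and Table 6 should add to 70.
- Add a sentence saying that 69 is the minimum after dropout under the individual-level formula, and that the planned number exceeds it.

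The cost is wording only. No pupils are needed beyond those already planned in Table 5.
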